### **6.1.2 Duration of Response**

Duration of overall response: The duration of overall response is measured from the time measurement criteria are met for Complete Response or Partial Response (whichever is first recorded) until the first date that Stable Pain or Pain Progression is objectively documented.

The duration of overall CR is measured from the time measurement criteria are first met for CR until the first date that Partial Response is objectively documented.

Duration of stable pain: Stable Pain is measured from the start of the treatment until the criteria for Pain Progression are met, taking as reference the baseline measurements recorded just prior to treatment.

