**Figure 3: Helical TomoTherapy Unit**

### **1.3.7 STAT RT Workflow: Same Day CT Simulation, Treatment Planning, Treatment Delivery**

As previously stated, we have already developed a STAT RT workflow for same day palliation that requires approximately 6 hours, and is a highly coordinated conventional workflow with kVCT simulation, treatment planning, treatment plan quality assurance, and then delivery of conformal hypofractionated radiotherapy. All treatments are planned and delivered on FDA-approved systems. We have treated over 30 patients to date with this workflow, and preliminary results reveal rapid and durable palliation with minimal acute toxicity. This workflow allows patients to receive an entire course of palliative treatment from start to finish in 1 to 5 days, a process that conventionally takes 3 weeks. Since patients are billed for each individual treatment, requiring fewer treatments reduces health care costs in addition to being more convenient. With the STAT RT program we are now able to offer a unique workflow that delivers rapid, effective, and efficient palliative radiotherapy that is cost effective, less toxic, and more convenient for cancer patients and their families. The dose conformality of these treatments is excellent and will not be further optimized. In this pilot clinical trial, for the primary specific aim we will quantify patient outcomes following treatment with the current STAT RT workflow in an effort to determine its benefits and risks to patients. As a secondary aim, we will systematically evaluate and optimize the software necessary for the clinical implementation of the more efficient Scan-Plan-Treat STAT RT workflow.

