## **4.0 TREATMENT PLAN**

### **4.1 Schema**

|                                  | Tx                | Follow-Up         |                          |                          |                          |                          |                          |
|----------------------------------|--------------------------|--------------------------|--------------------------|--------------------------|--------------------------|--------------------------|--------------------------|
| Helical
TomoTherapy*: |                          |                          |                          |                          |                          |                          |                          |
| Assessments†:             |  |
| Week:                     | 0                 | 1                 | 4                 | 8                 | 12                | 26                | 52                |

\*1-5 helical TomoTherapy radiation treatments over 1-2 weeks

† Physical Exam (PE) and/or surveys

Treatment-related toxicity will be captured during treatment PEs and followup PEs.

- This is an investigator-initiated, prospective, non-randomized, multi-centered pilot phase II trial. The clinical trial will be open to accrual at UVA and CRH only.
- We anticipate that it will take approximately 24 months to accrue 30 patients to this pilot study, and each patient will plan to undergo 1 year follow-up.

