## **6.0 EVALUATION CRITERIA**

### **6.1 Response to Palliative Radiotherapy**

#### **6.1.1 Response Criteria According to the International Bone Metastases Consensus Group**

Complete Response (CR): Pain reduction to zero AND OMED\* stable or reduced

Partial Response (PR): Pain reduction by two scores or more AND OMED\* stable or reduced.  
OR  
Stable pain AND OMED\* reduction by 25% or more

Pain Progression (PP): Pain increase by two scores or more AND OMED\* stable or increased.  
OR  
No change in pain AND OMED\* increased by 25% or more (or start of morphine use after the baseline or epidural pain treatment at follow-up)

Stable Pain (SP): Stable pain AND stable OMED\*

OMED = Oral Morphine Equivalent Dose

\* The total OMED intake over the most recent 72 hours will be calculated at each evaluation.

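### Section 6.1.2 ends complete response only at a documented Partial Response, so a CR can outlast the overall response that contains it or have no end date

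*Combined protocol and SAP*

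**What the plan says.** Section 6.1.2 gives two adjacent duration rules.

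- **Overall response** starts at the first CR or Partial Response (PR), whichever comes first, and runs "until the first date that Stable Pain or Pain Progression is objectively documented".
- **Complete response**: "The duration of overall CR is measured from the time measurement criteria are first met for CR" and it runs "until the first date that Partial Response is objectively documented". Neither Stable Pain (SP) nor Pain Progression (PP) is named as an end of CR, and there is no wording such as 'or worse'.

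Section 6.1.1 defines four separate categories. CR begins "Pain reduction to zero AND OMED" and also requires the opioid dose to be stable or lower. SP is "Stable pain AND stable OMED". PR and PP have their own criteria, built on a change of two points in pain or 25% in OMED.

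Section 7.3 assigns the category at each evaluation by comparing that visit's BPI worst pain and OMED with the pre-treatment values, not with the previous visit. Evaluations are at weeks 1, 4, 8 and 12 and at 6 and 12 months (section 7.1, primary aim; the schema in 4.1 shows the last two as weeks 26 and 52). For response, 7.3 plans only the percentage of patients in each category at each evaluation.

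**The concern.** CR is one form of overall response, so it should never last longer than the response it belongs to. The two rules break that relation because they stop at different events. A patient whose pain returns to its baseline level has lost both CR and response. Yet only the overall-response clock stops at that visit. The CR clock waits for a PR that may come later, after the relapse, or not at all.

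What is at stake is any CR duration that the investigators report. Section 6.1.2 is the only rule in the documents for computing one. Its error flatters the treatment for patients who lose CR without a recorded PR visit. Section 1.3.7 already describes the experience to date in terms of durability ("preliminary results reveal rapid and durable palliation with minimal acute toxicity"), so a reported duration would be read with interest.

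**Working it through.** The plan states no figure for this point, so there is none to reproduce. The check applies the rules as written.

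**Step 1. Can CR be followed directly by SP or PP?** Take a baseline worst pain of 5 and a stable OMED, and read stable pain as a change of less than two points (an assumption, since 6.1.1 gives no number for it). Under 6.1.1, measured against baseline as 7.3 requires:

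| Worst pain at visit | Category |
|---|---|
| 0 | CR |
| 1 to 3 | PR |
| 4 to 6 | SP |
| 7 or more | PP |

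A patient at 0 on one visit and at 5 on the next goes from CR to SP with no PR visit between. With a baseline of 3, only a score of 1 is PR, 2 to 4 is SP and 5 or more is PP.

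**Step 2. Worked sequences within weeks 1 to 12.** Duration = end week − start week.

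| Week 1 | Week 4 | Week 8 | Week 12 | Overall response | CR as written | CR if ended at first PR, SP or PP |
|---|---|---|---|---|---|---|
| CR | CR | SP | PR | 8 − 1 = 7 weeks | 12 − 1 = 11 weeks | 8 − 1 = 7 weeks |
| PR | CR | PP | PR | 8 − 1 = 7 weeks | 12 − 4 = 8 weeks | 8 − 4 = 4 weeks |
| CR | CR | PP | PP (and at every later visit) | 8 − 1 = 7 weeks | no end date | 8 − 1 = 7 weeks |

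In the first two rows the CR ends at a PR recorded four weeks after the response itself was declared over.

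**Step 3. Is this a rare corner of the definition?** Four categories at six visits give 4^6 = 4,096 possible sequences. In 2,346 of them CR starts inside a running overall response that later ends. Under the written rules:

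- CR ends later than the overall response, or never ends, in 1,698;
- of these, CR has no end date in 846, which leaves 1,698 − 846 = 852 with a finite but too late end;
- in the other 2,346 − 1,698 = 648, CR does not outlast the response.

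If CR ends at the first PR, SP or PP, the count of 1,698 falls to 0. These are counts of logical possibilities and say nothing about how often each would occur.

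**Step 4. Direction.** The corrected rule stops at the earliest of three events, one of which is the written rule's only event. The written CR duration is therefore always equal to or longer than the corrected one.

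**The case against.** The strongest reply is that nothing planned depends on this sentence. The primary objectives in 2.1 do not include duration of CR, and 7.3 plans category percentages by visit, with no median, mean or survival-type estimate of duration. That stands, and it limits the consequence. A second reply is that the authors surely meant PR or worse. That is probably so, but the text does not say it, and the preceding sentence lists its own end events explicitly.

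A reader might also infer more than the documents support:

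- *That the rule distorts a median CR duration, because few CRs are expected among 30 patients.* The plan calls for no such median, and the documents give no expected CR rate.
- *That CR can be overstated six-fold.* With CR at week 4, SP at week 12 and no PR by week 52, one might set 52 − 4 = 48 weeks against 12 − 4 = 8. But 6.1.2 does not say that CR is cut off at the last visit; the rule simply gives no end date.
- *That it undermines the durability argument in 1.3.1 (13.6 months against 3 to 6 months).* Those figures concern pain relief in general. The nearer quantity here is overall response, whose end events are sound on this point.
- *That the long gaps after week 12 (14 and 26 weeks) are the cause.* They make an unseen PR easier, but the contradiction already arises within weeks 1 to 12. Categories at 6 and 12 months are also uncertain: the table in 5.1 marks no opioid logbook evaluation at those visits, although 7.1 lists analgesic use there.

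**Conclusion.** The CR duration rule in 6.1.2 is wrong as written. It is a stated rule that gives a self-contradictory result, not a missing detail, and no other section repairs it. In the main example CR is 11 weeks inside an overall response of 7 weeks, an excess of 4 weeks; where no PR follows, CR has no end date at all. The error can only overstate CR.

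The conclusion rests on a literal reading of 6.1.2, on the baseline comparison in 7.3 and, for the pain-score illustration, on stable OMED and stable pain meaning a change of less than two points. How often such sequences would occur cannot be judged from the documents. The sample size, the planned tests and the by-visit response percentages in section 7 are unaffected. The sentence should be corrected before any CR duration is reported.

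**What to change.** In 6.1.2, keep the start of the CR duration and replace its end with: *until the first evaluation at which the CR criteria no longer hold (Partial Response, Stable Pain or Pain Progression)*.

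This restores the logical order of the two durations. It needs no extra patients, visits or data, and changes no treatment rule. The cost is one sentence in an amendment, and reported CR durations may be shorter than under the present wording.

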### **6.1.3 Response Review**

The endpoints in this study are all quantitative based on validated surveys and pain scores that are reported by the patients. Thus, we do not feel that a review by an expert independent of the study is necessary or valuable.

## **6.2 Toxicity and Safety**

All patients who receive treatment on this protocol will be evaluable for toxicity using the National Cancer Institute (NCI) Common Terminology Criteria for Adverse Events (CTCAE) Version 4 and the RTOG Late Radiation Morbidity Scoring Criteria at time points indicated in the Time and Events table in Section 5.1.

## **7.0 STATISTICAL CONSIDERATIONS**

### **7.1 Study Design**

This is an investigator-initiated, prospective, non-randomized, single-centered phase II clinical trial. This clinical trial will have a primary aim of determining outcomes of patients treated with a conformal hypofractionated STAT RT treatment utilizing widely accepted surveys and questionnaires and clinical examinations. The secondary aim is to collect clinical data to optimize software integration to develop the Scan-Plan-Treat STAT RT workflow that will make the entire process much quicker and efficient for the patient and clinic. The University of Virginia diagnoses almost 3000 cancers annually and we treat

approximately 80 patients with osseous metastases each year in the Department of Radiation Oncology. We anticipate it will take approximately 18 months to accrue 30 patients to this pilot study.

**1) Primary Aim: Evaluation of Outcomes of Patients with Osseous Metastases Treated with STAT RT**

We will recruit 30 cancer patients with 1-3 painful osseous metastatic lesions (target sites) requiring opioid medication who are candidates for palliative radiation therapy. Patients will receive 2-5 fractions of 5-10 Gy (minimum BED of 25 Gy) of conformal radiation therapy delivered to the target sites via the Helical TomoTherapy system using the STAT RT workflow. Patient pain, analgesic use, function, quality of life, and satisfaction will be recorded prior to treatment, at 1 week, 4 weeks, 8 weeks, 12 weeks, 6 months, and 12 months after therapy using the following measures:

- a) The Brief Pain Inventory (BPI)
- b) Patients will keep an analgesic use logbook and have their doses converted into Oral Morphine Equivalent Doses (OMED).
- c) Treatment response will be measured by the guidelines set forth by the International Bone Metastases Consensus Group as described in Section 6.1.1.
- d) The FACT-BP and FACT-G questionnaires
- e) Karnofsky Performance Scale (KPS)
- f) Patient Satisfaction will be measured by a modified FACIT-TS-BTCSQ survey.

Radiation-induced treatment related toxicities will be captured during treatment and at the above time points and graded using the CTCAE Version 4.0 and the RTOG Late Radiation Morbidity Score Criteria.

**2) Secondary Aim: Optimization of Software Integration for Scan-Plan-Treat Workflow**

Several secondary investigational aims will be studied that will not be used in direct patient care but are essential in further streamlining the STAT RT workflow. These components will not subject the patient to any additional inconvenience or risk. Standard patient-specific quality assurance will be performed on a Matrixx ion chamber array.

**a) Optimization of Novel Image Co-registration Workflow**

The standard two step image co-registration process of contoured diagnostic images to kVCT simulation scans and then kVCT simulation scans to MVCT image guidance scans will be used to treat all patients. We will then experimentally co-register the contoured diagnostic images directly to the MVCT scan, and the PTV and OAR contours generated onto the MVCT scan by both methods will then be compared.

To evaluate the conventional and the experimental image registration flows, the two registration flows will be compared in the following manner:

- Gross tumor volumes (GTVs) will be generated from both the conventional and experimental image registration flows. The differences in volume and the distances between the two centers of the GTVs will be used to evaluate the similarity of the two GTV contours.
- Spinal cord contours will also be generated from both registration flows. The point of the spinal cord that has the shortest distance to the center of the GTV will be identified for each contour. The distance between the points from the two registration flows will be used to evaluate the similarity of the two cord contours. The volumes of the two cords will also be compared.
- Quantitative evaluation of the contours will be performed using the Dice index. Dice index is defined as the overlapping volume of two structures divided by the average volume of the two. Clearly, Dice index is 1 if the two structures are identical and 0 if they do not share any voxel. Dice index will be calculated in Velocity for contours generated on conventional and experimental image registration flows. Dice indices of 0.8 or higher are acceptable based on literature (61).

**b) Treatment Planning Speeds**

We will determine the speed of radiation treatment planning with our current clinical system and compare this to the speed of planning with newer in-development algorithms running on next generation computers with graphic processing units (GPUs). Since highly conformal radiation treatments must be routinely calculated in a few minutes for the Scan-Plan-Treat STAT RT workflow, we will determine if the treatment planning with GPUs is fast enough for clinical implementation (i.e. can be done in approximately 5 minutes). If not, we will optimize the planning process in collaboration with TomoTherapy, Inc to increase the speed of planning.

**c) Exit Radiation Dose Verification**

In-development software provided by TomoTherapy Inc.® will be used to measure the exit dose fluence, backproject this fluence as entrance fluence, and then calculate the patient dose on the MVCT scan. This software will be further optimized and refined on this clinical trial. All patients' radiation treatment plans will undergo standard of care phantom-based quality assurance measurements. The phantom exit dose will also be calculated via this software in this optimization process. By comparing the values obtained with the software to the calculated treatment plan and phantom measurements, we hope to optimize this novel radiation dose verification software to +/- 3% calculated to delivered dose. Preliminary data shows that we are already at +/- 5% calculated to delivered dose (53).

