One drawback from the dose reconstruction method mentioned above is that it relies on the accurate knowledge of the patient geometry and attenuation at the time of the treatment. This information may not be fully available nor accurate. This leads to the ambiguity in determining whether a discrepancy observed from the dose reconstruction is real (caused by the machine) or merely an artifact caused by the patient such as weight loss or

positional changes. To remedy this, we have developed a method to detect if the multi-leaf collimator (MLC) is open or close based on the sharp change in the exit fluence independent of the patient attenuation (54). In addition, the LINAC output and gantry angles during treatment are measured independently for quality assurance. Combining those data, the impact of deviations during the treatment delivery can be evaluated through the MCL dose calculation. The CT detector clinical data collected will also be used to optimize this in-development software.

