#### **1.4 Preliminary Studies**

We have performed significant preliminary research into optimizing each of the necessary steps for clinical implementation of the Scan-Plan-Treat STAT RT workflow as detailed below. Preliminary clinical data will be collected from patients treated with STAT RT on this protocol to optimize the software required to develop the more efficient Scan-Plan-Treat STAT RT workflow. A Scan-Plan-Treat workflow will not be used on this clinical protocol.

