**2.2 Secondary Objectives**

Our secondary objectives are to optimize the integration of commercially available and in-development software that are needed to develop a Scan-Plan-Treat STAT RT workflow. Specifically, we plan to:

- 2.2.1** Optimize CT-detector-based exit dose measurement algorithms for quality assurance and compare them to traditional phantom quality assurance methods.
- 2.2.2** Optimize rigid and deformable co-registration of pre-contoured diagnostic image sets to MVCT simulation scans and compare the accuracy to the conventional method in which the same pre-contoured diagnostic image sets are co-registered to kilovoltage CT (kVCT) simulation images and then kVCT simulation is co-registered to the MVCT scan.
- 2.2.3** Validate an in-house infrared tracking system and monitor patient motion during treatment for all patients treated a ECCCC.

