**d) Infrared Motion Tracking System (UVA patients only)**

An in-house developed infrared motion tracking system will be optimized at the Emily Couric Cancer Center. The system will initially be validated on 10

healthy volunteers who will be instructed to lie still on the couch for 10 minutes. Following that, a small couch motion of 1-5 mm will be introduced in the x, y and z directions and compared with the motion detected by the infrared cameras. After the system is validated with the healthy volunteers, it will then be used to monitor the intra-fractional motion of patients treated on this protocol during treatment. We anticipate having to modify/edit the software code during clinical implementation.

All patients undergoing treatment at UVA will have “set up” skin marks placed as is standard of care for laser alignment of the patient prior to MVCT scan image guidance, which is then used for finer (generally millimeter) adjustments of internal target volumes. Following scanning we will note the position of the lasers with respect to the set up skin marks, and at the completion of treatment we will again measure the location of the set up marks to the lasers. With this data we can determine if the patient had moved after the image guidance MVCT or during treatment, and we will compare this with data from the infrared tracking system. This system does not utilize ionizing radiation, add additional burdens or constraints, cause any discomfort or side effects, and is completely noninvasive. In reality, an additional layer of safety is added to the STAT RT treatment as any unexpected patient motion will be monitored and reported. We anticipate that this system will be able to accurately track patients with +/- 2-3 mm of motion accurately.

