## **7.2 Sample Size and Accrual**

We performed calculations to detect a change in patients’ BPI pain scores before and after treatment using the Wilcoxon signed-rank test. Using the software G\*Power 3.1.2 (University Kiel, Germany) the following calculations were made. To detect a mean change of 2 units on the BPI scale with a standard deviation of 3, and achieve a 2-sided alpha of 0.05 with 80% power, a sample size of 21 is needed. Most studies report a mean improvement in pain scores of about 3.5. (32). Thus we anticipate an improvement by at least 3 on the BPI in our study, which should be adequately powered with 30 patients.

Since we have had accrual from prior studies of about 20 patients a year and this is a pilot study, we thought that a sample size of 30 subjects would be realistic for accrual and provide the necessary patient data for optimization of the software systems. We treat approximately 30 patients with osseous metastases annually at UVA with palliative radiotherapy. We anticipate an accrual rate of 20 cases per year over 18 months. Since the power analysis requires a sample size of

21, accrual of 30 subjects would allow for dropouts and still have sufficient power.

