### **7.3 Data Analyses Plans**

Treatment response as defined by International Bone Metastases Consensus Group will be determined for each patient. As described in Section 6.1.1, pain intensity as defined by the BPI and opiate use as quantified by the OMED will be used to categorize patients as having: Complete Response, Partial Response, Pain Progression, Stable Pain. At each evaluation, the patient's BPI and OMED at that visit will be compared to the pre-treatment levels. The "Worst Pain" score from the patient's BPI will be used to evaluate for treatment response. Patient response does not require a statistical analysis. The percentage of patients in each response category at each evaluation will be reported.

Patient pain will be recorded using the BPI before treatment and at designated evaluations after treatment. Pain scores before and after treatment will be compared using a Wilcoxon signed ranks test to determine if there is a statistically significant difference. Example: Pre-treatment vs. 1 week, Pre-treatment vs. 4 weeks, etc.

Analgesic use will be recorded by requiring each patient to keep a logbook of their analgesic intake. Their opiate intake for the last 72 hours will be converted to OMED at each evaluation and used in the categorization of treatment response. The difference between their OMED before and after treatment will be compared using paired two-sample t-tests.

Patients' functional status will be determined using the Karnofsky Performance Scale at each evaluation. The difference between the KPS before and after treatment will be compared using a Wilcoxon signed ranks test.

Patients' quality of life will be measured using FACT-BP and FACT-G scores at each evaluation. The difference between the FACT scores before and after treatment will be compared using a Wilcoxon signed ranks test.

Patient satisfaction will be measured using a modified version of FACT - TS – BTCSQ. No statistical analysis will be required for reporting the results. The average scores from the satisfaction survey will be reported.

To evaluate the CT detector dose calculations, the delivered radiation dose obtained using the phantom quality assurance will be compared to the exit radiation dose quality assurance calculation. The calculated dose and delivered dose for each patient will be compared using a paired two-sample t-test, and the % difference in dose will be reported.

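### Objective 2.2.1 tunes the exit-dose software on the trial's patients and reports its agreement on the same patients, with no version lock or held-out data, so that agreement cannot support a claim of equivalence to phantom quality assurance.

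*Combined protocol and SAP*

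**What the plan says.** Four parts of the plan make the trial's own patients the tuning set for the exit-dose software.

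- Section 7.1 c): "This software will be further optimized and refined on this clinical trial". The method is to compare the software's values with the treatment plan and the phantom measurements, and the target is stated: "we hope to optimize this novel radiation dose verification software to +/- 3% calculated to delivered dose". The starting point given there is +/- 5%.
- Section 1.3.9, item 5, says that clinical data will be collected to go on optimising the dose-reconstruction algorithm. Of the companion leaf-opening method it says: "The CT detector clinical data collected will also be used to optimize this in-development software".
- Section 1.4: "Preliminary clinical data will be collected from patients treated with STAT RT on this protocol to optimize the software required".
- Section 7.2 justifies the sample size partly on this ground: "a sample size of 30 subjects would be realistic for accrual and provide the necessary patient data for optimization of the software systems".

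Section 7.3 then sets the accuracy analysis. Phantom dose is compared with the exit-dose calculation: "The calculated dose and delivered dose for each patient will be compared using a paired two-sample t-test", and the percentage difference is reported.

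Section 1.5 gives the result a confirmatory use. It says that equivalence to phantom measurement has to be confirmed, and that once this is proved the phantom step could be dropped in future. The Study Overview also describes the comparison as validation.

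On the infrared system, Section 7.1 d) describes a validation on 10 healthy volunteers, followed by use in patients, and adds: "We anticipate having to modify/edit the software code during clinical implementation".

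**The concern.** When a tool is adjusted until it agrees with a reference, its agreement on the data used for the adjustment is not an estimate of its agreement in the next patient. Here the quantity being improved and the quantity being reported are the same, in the same patients. The documents mention no version lock, held-out group, cross-validation, record of the version used for each patient, or rule on reprocessing.

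What is at stake is the conclusion that Section 1.5 wants to draw. The hoped-for +/- 3% is also the tolerance that Section 1.3.9 gives for current phantom measurement, so a modest understatement of error could decide whether the new method appears to match the old one. Treatment in this trial is not at stake, because standard phantom quality assurance is kept for every patient.

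**Working it through.** **The plan's own figures.** The plan gives no sample size or precision for software accuracy. Its only calculation, 21 patients for the change in BPI pain, reproduces: the Wilcoxon signed-rank test by asymptotic relative efficiency, with d = 2/3 and two-sided 0.05, gives N = 21 and power 0.808. It has no bearing on this point.

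**Inputs from the documents.** n = 30 patients (7.2); target +/- 3% and starting value +/- 5% (7.1 c); 2-5 fractions per patient. **Assumptions.** The +/- figure is read as a root-mean-square (RMS) spread of the percentage difference. Tuning behaves like a least-squares fit of k quantities. The documents do not state k, so a range is shown.

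**Case A: all stored data are reprocessed with the final, tuned version.** The expected in-sample RMS error is the true spread times sqrt(1 - k/n). For new patients it is about the true spread times sqrt(1 + k/n). The ratio is sqrt((n + k)/(n - k)). A simulation (4,000 runs per k) that also redraws the new patients' characteristics gives slightly larger ratios for the larger k.

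| k | Formula ratio | Reported 3% becomes (formula) | Simulated ratio | Reported 3% becomes (simulation) |
|---|---|---|---|---|
| 1 | sqrt(31/29) = 1.03 | 3.1% | 1.036 | 3.1% |
| 3 | sqrt(33/27) = 1.11 | 3.3% | 1.107 | 3.3% |
| 5 | sqrt(35/25) = 1.18 | 3.5% | 1.199 | 3.6% |
| 10 | sqrt(40/20) = 1.41 | 4.2% | 1.524 | 4.6% |

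Three further checks:

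- Choosing the best of several equally accurate versions, with no fitting at all, has a similar effect. A reported 3% corresponds to a true 3.3% for the best of 2 and 3.8% for the best of 10 (20,000 runs, errors independent between versions).
- If a single additive dose offset is tuned on the 30 patients, the mean difference is zero by construction. The planned paired t-test then returns p = 1 whatever the accuracy in new patients.
- Overfitting alone could not plausibly turn 5% into 3%. That needs 1 - k/30 = (3/5)^2 = 0.36, so k is about 19.

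**Case B: each patient keeps the result of the version then in use.** Pooling an early version at 5% with a final one at 3% gives sqrt(f x 25 + (1 - f) x 9), where f is the fraction on the early version: 3.6% for f = 0.25, 4.1% for f = 0.50 and 4.6% for f = 0.75. The pooled figure is worse than the final version's 3% and describes no version that would be carried forward.

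The plan does not say which case applies, so the direction of the error is not known either.

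**The case against.** The strongest reply is that this is development work. It is a secondary aim of a pilot, Section 7.1 describes its purpose as optimising software, the Scan-Plan-Treat workflow is not used on this protocol, and phantom measurement is not replaced. All of that stands, and it limits the weight of the point. It does not remove it, because Section 1.5 speaks of confirming and proving equivalence.

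A reader might infer more than the documents support, in three ways.

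- *That the agreement will be both too good and a mixture of versions.* The two largely exclude each other: case A gives optimism without mixture, and case B gives a mixture that looks worse than the final version. Both arise together only if the software is retuned in batches and post-tuning values are reported.
- *That all three secondary objectives share the defect.* Tuning to the reported outcome is documented only for 2.2.1. Objective 2.2.2 does pair the two verbs ("Optimize rigid and deformable co-registration of pre-contoured diagnostic image sets to MVCT simulation scans and compare the accuracy to the conventional method"), but Section 7.1 a) describes only a comparison of two registration flows in commercially available software, with no setting adjusted to the Dice index or the centre distances. Objective 2.2.3 has a prior volunteer check against introduced couch motions of 1-5 mm, does not include the Culpeper patients, and is not said to be tuned to the laser and skin-mark readings. What remains there is that code edited after the volunteer check is not revalidated.
- *That the larger error figures are the expected ones.* They need 5-10 tuned quantities. With 1-3 the understatement is small. If tuning used fractions (30 x 2 = 60 to 30 x 5 = 150), the formula with k = 5 gives sqrt(65/55) = 1.09 down to sqrt(155/145) = 1.03. This is a lower bound, since fractions cluster within patients.

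It is also fair to say that holding patients back has a price, and that for small k the wider interval exceeds the bias removed. That interval is at least visible to the reader, whereas the bias is not.

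**Conclusion.** The point holds for objective 2.2.1. The same patients and the same criterion serve for tuning and for reporting, with no version lock or independent data. The reported agreement may be optimistic or may blend versions, and either way it does not support the equivalence statement in Section 1.5. Under the least-squares assumption, a reported 3% on 30 patients corresponds to about 3.1% to 4.6% in new patients as k runs from 1 to 10. That range is an illustration, not an estimate, because the number of tuned quantities and the reprocessing rule are not stated. For 2.2.3 the point is narrower: edits after the volunteer validation leave the version used in patients undefined. This is a cheap improvement to the plan and does not affect treatment in the trial.

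**What to change.** In Sections 7.1 c) and 7.3:

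1. Record the exit-dose software version used for each patient.
2. Lock a version at a prespecified point. The 24 patients and 347 fractions already studied (Section 1.4) could serve as development data, if still accessible, and allow an earlier lock.
3. Base the reported percentage difference, and any equivalence statement, only on patients not used to tune the locked version. Where tuning is an automated refit, leave-one-patient-out results from stored detector data would serve instead. They do not suit code edited by hand.
4. Label all other results as development estimates.

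In Section 7.1 d), number the infrared code versions after the volunteer validation, and report agreement only for UVA patients run on the final version.

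**Cost.** SAP wording and version control, with no new patients or procedures. The price is precision. The 95% confidence interval for an SD runs from 0.80 to 1.34 times the estimate with 30 test patients, 0.73 to 1.58 with 15, and 0.69 to 1.83 with 10. An estimate of 3% would thus carry about 2.4-4.0% with 30 patients and 2.2-4.7% with 15. The lock point should be chosen with that trade-off in view; an even split is not required.
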